## Protocol Synopsis

## ASPiRE Antiplatelet Strategy for Peripheral Arterial Interventions for Revascularization of Lower Extremities

PI	Name: [name]
	[contact]
	Email: [contact]
TRIAL OBJECTIVE	
Primary Objective	To evaluate whether clopidogrel 75 mg daily on a background of aspirin 81 mg/d for U.S. sites (75-100 mg/d for international sites) for clinically indicated duration or an additional 12 months will lead to an increased rate of primary patency, limb salvage, non-fatal myocardial infarction (MI), ischemic stroke, and survival, in patients receiving endovascular treatment of PAD at end of study treatment
Control Arm	clopidogrel 75 mg daily on a background of aspirin 81 mg/d for U.S. sites (75-100 mg/d for international sites) for clinically indicated duration with a minimum of 30 days.
Test Arm (as applicable)	clopidogrel 75 mg daily on a background of aspirin 81 mg/d for U.S. sites (75-100 mg/d for international sites) for clinically indicated duration + 12 months
Endovascular	Iliac
interventions included	Femoropoliteal
	Below-the knee
TRIAL DESIGN	
Trial Design	Prospective, two-arm, multicenter randomized clinical trial.
PlannedNumber of Subjects	202 subjects will be enrolled in each arm (total subjects = 404)
Clinically indicated dual	Clinically indicated DAPT duration will be based on the longest pre-
antiplatelet therapy	discharge following an index peripheral intervention procedure,
(DAPT) duration	DAPT duration. This will be determined based on: peripheral
	intervention device IFUs, preceding coronary intervention, acute
	coronary syndrome or other guideline-based clinical or device

	specific DAPT durations.
PlannedNumber of Sites / Countries	Approximately 18 investigational centers in the U.S are expected to participate.
	No center will be allowed to enroll more than 40% of planned total enrollment.
Primary Endpoint	Primary Endpoint (subject-based): The first occurrence of index limb arterial occlusion, surgical intervention, endovascular intervention, amputation of the affected limb (vessel occlusion or failure), MI, ischemic stroke or death at 12 months from index procedure or end of study treatment, whichever is longer
Secondary Endpoints	Secondary Endpoints through end of study treatment:
	• The first occurrence of any individual component of the primary endpoint
	• First occurrence of the following during follow-up: cardiovascular death, or MI, or ischemic stroke, or any amputation above the ankle.
	• Severe bleeding defined according to the Global Utilization of Streptokinase and Tissue plasminogen activator for Occluded coronary arteries (GUSTO) classification
Tertiary Endpoints	• Moderate bleeding defined according to the Global Utilization of Streptokinase and Tissue plasminogen activator for Occluded coronary arteries (GUSTO) classification
Randomization	
 
Patients scheduled for a planned discharge will be randomized on a 1:1 basis using a computerized central randomization portal available through RedCap® to either of the following treatment groups:         
 
ASA (81 mg U.S. sites; 75-100 mg international sites) + clopidogrel: for clinically indicated duration (control arm)
 
ASA (81 mg U.S. sites; 75-100 mg international sites) + Clopidogrel 75mg: for clinically indicated duration +12m (treatment arm)
 
 
 
Randomization will be performed at the within 2 weeks of an eligible procedure
 

Follow-up schedule	All potential subjects will be evaluated for enrollment after the index procedure pre-discharge or within 14 days of the procedure. Follow- up schedule will include patient visits at 30 days and q6 months till the end of study treatment The trial will be considered complete with regard to the primary endpoint after all enrolled subjects have

	completed a 12-month or end of study treatment follow-up evaluation, have died, have a documented premature discontinuation, or whose follow-up window has closed. Follow-up window is $\pm 7$ days for the 30-day visit and $\pm 15$ days for all other visits.
Key Inclusion Criteria	
 
General:
 
Signed informed consent
 
At least 18 years old
 
Documented symptomatic iliac, femoropopliteal (FP) or below-the knee artery (BTK) atherosclerotic disease (Rutherford/Becker category 2, 3 or ≥4)
 
Undergone clinically indicated uncomplicated endovascular intervention to one or more locations of the iliac, femoropopliteal below-the knee arteries
 
Estimated survival ≥1 year in the judgment of the primary operator
 
Pre-index procedure use of ASA, clopidogrel or both at any dose
 
Angiographic:
 
De novo or restenotic lesions in the common and/or external iliac artery, superficial femoral artery (SFA), popliteal artery, tibio-peroneal (TP) trunk, anterior tibial (AT) artery, peroneal artery (PA) or posterior tibial (PT) artery (applies to all target lesions if multiple)
 
Subjects with multiple planned procedures can be enrolled after the completion of the last planned procedure.
 

Key Exclusion Criteria	
 
General:
 
Complicated qualifying procedure (perforation, flow limiting dissection, distal embolization requiring re-intervention, need for repeat endovascular, surgical revascularization, amputation or blood transfusion prior to hospital discharge following index procedure
 
Extended hospital stay >7 days following the index procedure
 
Allergy to aspirin or clopidogrel
 
Life expectancy less than 12 months due to other medical comorbid condition(s) that could limit the subject's ability to participate in the trial, limit the subject's compliance with the follow-up requirements, or impact the scientific integrity of the trial
 
Known hypersensitivity or contraindication to contrast dye that, in the opinion of the investigator, cannot be adequately pre-medicated.
 
Intolerance to antiplatelet, anticoagulant, or thrombolytic medications
 
Platelet count <90,000 mm^3 or >600,000 mm^3
 

	• Serum creatinine >2.5 mg/dL
	• Dialysis-dependent end stage renal disease
	Pregnancy
	• Current participation in another drug or device trial that requires
	interruption of dual-antiplatelet therapy with aspirin or
	clopidogrel for the duration of this study
	• Planned surgeries, endovascular or other non-vascular or cardiac
	procedures
	Warfarin or other chronic oral anticoagulant use
	• Contraindication(s) to the use of antithrombin or antiplatelet
	agents (history of intra-cerebral bleed, presence of intracerebral
	mass, recent or <6 weeks gastrointestinal bleed, blood
	transfusion within the last 6 weeks, any trauma requiring surgery
	or blood transfusion within the last 4 weeks or any surgical
	procedure within the last 4 weeks.
	Angiographic:
	• Endovascular intervention to iliac, FB or BTK
	artery bypass graft
	Persistent, intraluminal thrombus of the
	proposed target lesion at the completion of
	the index procedure
	• Perforated vessel as evidenced by extravasation of contrast media
	
 
Vascular graft, aneurysm or postsurgical stenosis of the target vessel
 

Multiple Interventions	Multiple interventions during an index procedure will be allowed as
During Index Procedure	long as the procedure is deemed successful and uncomplicated by the
	primary operator and no additional procedures are planned
Statistical Methods	
Sample size parameters	• The occurrence of the primary endpoint is expected
Sampre Size parameters	to be approximately 49% at 12 months in the
	control group 
	
 
A 30% relative risk reduction in the incidence of primary
 

	endpoint would be clinically important
	
 
To detect a 30% relative reduction in the 1-year primary
 

	event rate from $49\%$ to $34.0\%^{17}$ with $80\%$ power at the two sided 05 significance level assuming a 12 month
	two-sided, .05 significance level, assuming a 12-month
	two-sided, .05 significance level, assuming a 12-month recruitment period and a 1 0 % dropout rate at 1 year, a total
	two-sided, .05 significance level, assuming a 12-month recruitment period and a 1 0 % dropout rate at 1 year, a total of 404 (368+36) patients will be randomized (202 in each
	two-sided, .05 significance level, assuming a 12-month recruitment period and a 1 0 % dropout rate at 1 year, a total of 404 (368+36) patients will be randomized (202 in each group) and followed-up for endpoints for 12 months or until
	two-sided, .05 significance level, assuming a 12-month recruitment period and a 1 0 % dropout rate at 1 year, a total of 404 (368+36) patients will be randomized (202 in each
Statistical analysis	two-sided, .05 significance level, assuming a 12-month recruitment period and a 1 0 % dropout rate at 1 year, a total of 404 (368+36) patients will be randomized (202 in each group) and followed-up for endpoints for 12 months or until end of study treatment, whichever is longer
Statistical analysis	
 
two-sided, .05 significance level, assuming a 12-month recruitment period and a 1 0 % dropout rate at 1 year, a total of 404 (368+36) patients will be randomized (202 in each group) and followed-up for endpoints for 12 months or until end of study treatment, whichever is longer
 
Continuous variables will be summarized as mean±standard
 

Statistical analysis	
 
two-sided, .05 significance level, assuming a 12-month recruitment period and a 1 0 % dropout rate at 1 year, a total of 404 (368+36) patients will be randomized (202 in each group) and followed-up for endpoints for 12 months or until end of study treatment, whichever is longer
 
Continuous variables will be summarized as mean±standard deviation and compared using the t-test or the Wilcoxon rank-
 

Statistical analysis	
 
two-sided, .05 significance level, assuming a 12-month recruitment period and a 1 0 % dropout rate at 1 year, a total of 404 (368+36) patients will be randomized (202 in each group) and followed-up for endpoints for 12 months or until end of study treatment, whichever is longer
 
Continuous variables will be summarized as mean±standard deviation and compared using the t-test or the Wilcoxon rank-sum test, as appropriate
 

Statistical analysis	
 
two-sided, .05 significance level, assuming a 12-month recruitment period and a 1 0 % dropout rate at 1 year, a total of 404 (368+36) patients will be randomized (202 in each group) and followed-up for endpoints for 12 months or until end of study treatment, whichever is longer
 
Continuous variables will be summarized as mean±standard deviation and compared using the t-test or the Wilcoxon rank-
 

Statistical analysis	
 
two-sided, .05 significance level, assuming a 12-month recruitment period and a 1 0 % dropout rate at 1 year, a total of 404 (368+36) patients will be randomized (202 in each group) and followed-up for endpoints for 12 months or until end of study treatment, whichever is longer
 
Continuous variables will be summarized as mean±standard deviation and compared using the t-test or the Wilcoxon rank-sum test, as appropriate
 

	test	
•	For all comparisons a two-sided probability of <0.05 will be	
	considered statistically significant	
• All analyses were performed using the SAS 9.1 or recent		
	version (SAS Institute Inc., Cary, North Carolina)	
•	Primary endpoint will be assessed as per an intention-to treat principle	
•	Subsequent analysis will also be performed based on as treated	
	groups	
•	Pre-specified subgroup analyses will include:	
	Stent vs. non-stent groups	
	• DES vs. BMS	
	• Above and below-the knee treatment	
	Claudication vs. CLI groups	

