## 6. Trial endpoints

Clinical endpoints will be analyzed in all subjects who are enrolled, regardless of whether the trial treatment administered successfully completed for the desired duration. A subject will be considered enrolled in the trial when he/she is randomized to one of the treatment arms of the study. All endpoints are subject-based unless otherwise specified.

The primary endpoint is subject-based of the longer of a 12-month or end of study treatment endpoint of the first occurrence of index limb arterial occlusion, surgical intervention,

endovascular intervention, amputation of the affected limb (primary patency and limb salvage), MI, ischemic stroke or death (survival)

The secondary endpoints are subject-based on the longer of a 12-month or end of study treatment endpoints that include: (a) the first occurrence of any individual component of the primary endpoint, (b) the first occurrence of the following during follow-up: cardiovascular death, or MI, or ischemic stroke, or any amputation above the ankle and (c) severe bleeding defined according to the Global Utilization of Streptokinase and Tissue plasminogen activator for Occluded coronary arteries (GUSTO) classification

The tertiary endpoint is based on the longer of a12-month or end of study treatment moderate bleeding according to the GUSTO classification

Clinically indicated DAPT duration will be based on the longest pre-discharge following index peripheral intervention procedure DAPT duration. This will be determined based on: peripheral intervention device IFUs, preceding coronary intervention, acute coronary syndrome or other guideline-based clinical or device specific DAPT duration.

Study treatment will be discontinued at the first occurrence of a primary endpoint as defined in the table below. Patients, however, can resume taking aspirin, Clopidogrel, or both based on their provider's clinical decision.

Primary endpoint definition(s)	Secondary/Tertiary endpoint definition(s)
Occlusion of the target limb documented by any imaging procedure performed clinically	As described in section 6, except for:
any maging procedure performed ennearly	GUSTO bleeding criteria:
Any surgical or endovascular	1. Severe or Life-threatening: Intracerebral hemorrhage resulting in substantial
revascularization procedure on the index limb	hemodynamic compromise requiring treatment
Amputation above the ankle of the index	2. Moderate: Requiring blood transfusion but not resulting in hemodynamic

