## 7. Trial design

This is a prospective, multi-center, two-arm randomized clinical trial to evaluate whether clopidogrel 75 mg QD on a background of ASA 81 mg for U.S. sites (75-100 mg/d for international sites) for clinically indicated duration with a minimum of 30 days or an additional 12 months will lead to an increased rate of primary patency, limb salvage and survival, in patients receiving endovascular treatment of PAD.

Up to 404 subjects at approximately 18 centers in the United States are planned. Assuming 10% attrition at 12 months, enrollment of a minimum of 404 would yield at least 368 evaluable subjects for the longer of a12-month or end of study treatment endpoint. No center will be allowed to enroll more than 40% of the subjects.

A schematic of the trial design is provided in Figure 1.

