## 14. Sample size estimate

The occurrence of the primary endpoint is expected to be approximately 49% in the control group, derived on the basis of current literature review and preliminary data form XLPAD registry.

A 30% relative risk reduction in the incidence of primary endpoint would be clinically important. To detect a 30% relative reduction in the primary event rate from 49% to34%  with 80% power at the two-sided, 0.05 significance level, assuming a 12-month recruitment period and a 10% dropout rate at 1 year, a total of 404 patients will be randomized (202in each group) and followed-up for endpoints for longer of a 12-month or end of study treatment period.

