## **Primary Endpoint**

For the primary endpoint of 12-month composite of primary patency, limb salvage, MI, ischemic stroke and survival, with 95% confidence bounds will be calculated in the active arm and compared to control treatment duration. If this bound is less than that of control, then the primary endpoint will be considered met. All enrolled subjects are to be assessed for adverse events at follow-up visits. Assuming a maximum of 10% attrition due to non-compliance, loss to follow-up or death or non-compliance with follow-up, a minimum of 184 subjects in each arm are expected to be evaluable for the primary endpoint.

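### The primary endpoint window differs by arm and conflicts with Section 20's 12-month analysis, and the success rule there has no single meaning

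*Combined protocol and SAP*

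**What the plan says.** **Window, longer-of version.** The Synopsis primary endpoint ends with "MI, ischemic stroke or death at 12 months from index procedure or end of study treatment, whichever is longer". Section 6 says "The primary endpoint is subject-based of the longer of a 12-month or end of study treatment endpoint". Section 7 expects "at least 368 evaluable subjects for the longer of a12-month or end of study treatment endpoint", and Section 14 has patients "followed-up for endpoints for longer of a 12-month or end of study treatment period".

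**Window, 12-month version.** Section 20 (Primary Endpoint) opens "For the primary endpoint of 12-month composite of primary patency, limb salvage, MI, ischemic stroke and survival". The Synopsis sample size parameters also give the 49% control rate as a 12-month rate.

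**Treatment length.** Section 9 assigns control the clinically indicated duration, at least 30 days, and assigns the test arm that duration plus 12 months. Table 2 note 3 places the final treatment visit at completion of the assigned duration.

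**Test.** Section 20's criterion is "If this bound is less than that of control, then the primary endpoint will be considered met". Section 19 has a general chi-square rule for discrete variables and a two-sided 0.05 level, and Section 14 uses the same level. Section 16 allows censored-data models where appropriate, and Section 20 promises Kaplan-Meier plots. Neither names a test for the primary endpoint.

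**Secondary endpoints.** The Synopsis counts them up to the end of study therapy. Section 6 counts them to the later of that point and month 12.

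**The concern.** If the window follows the assigned therapy, the test arm is watched for longer than control, so it accrues more events even when the drug does nothing. The same holds for severe bleeding, which is central to judging longer dual therapy.

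The documents also leave two windows and an ambiguous success rule side by side. The result could then depend on a window and a method chosen after the data are seen.

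**Working it through.** **1. The plan's sample size.** Inputs from Section 14: 49% v 34%, two-sided 0.05, 80% power.
- n = [1.960·√(2·0.415·0.585) + 0.842·√(0.49·0.51 + 0.34·0.66)]² / 0.15² = 168.2, so 169 per arm.
- With continuity correction: (168.2/4)·[1 + √(1 + 4/(168.2·0.15))]² = 181.3, so 182 per arm, 364 in total.
- Allowing for 10% dropout: 364/0.9 = 404.4.

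This is close to the plan's 368 evaluable and 404 randomised. The plan is therefore sized as a comparison of two proportions at one common time. At 184 per arm, the test without continuity correction has 83% power.

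**2. Window lengths.** Control max(12, c), test c+12, gap min(c, 12). Both c and the window are counted from the index procedure.

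| c (months) | Control | Test | Gap |
|---|---|---|---|
| 1 | 12 | 13 | 1 |
| 3 | 12 | 15 | 3 |
| 6 | 12 | 18 | 6 |
| 12 | 12 | 24 | 12 |
| 18 | 18 | 30 | 12 |

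**3. The Section 20 rule with equal 12-month windows.** Exact binomial enumeration, 184 per arm, two-sided 95% Wald bounds p ± 1.96·√(p(1−p)/184). False success is at 49% v 49% (nominal 2.5% per side); power is at 49% v 34%.

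| Active upper bound lies below | False success | Power |
|---|---|---|
| control's observed rate | 8.0% | 94% |
| control's lower bound | 0.3% | 57% |
| control's upper bound | 48% | >99% |

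This step needs no assumption about c or late hazard.

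**4. Raw proportions over the longer-of window.** Assumptions: every patient has the same c, and the hazard after month 12 is f times the first-year hazard. The documents give neither c nor f. For c up to 12, control stays at 49%. The test arm is 1 − 0.51^((12+fc)/12) with no effect, and 1 − 0.66^((12+fc)/12) with the planned effect.

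Example, f = 0.25 and c = 12, no effect: 1 − 0.51^(15/12) = 56.9%. The null standard error is √(2·0.5295·0.4705/184) = 0.0520, and the unpooled one is 0.0519. The chance of significant harm is Φ((0.079 − 1.96·0.0520)/0.0519) = 33%.

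| f | False harm at c = 1/3/6/12 | Power at c = 1/3/6/12 |
|---|---|---|
| 0 | 2.5% throughout | 83% throughout |
| 0.25 | 3/6/12/33% | 80/74/62/37% |
| 1 | 8/33/81/>99% | 70/37/7/0% |

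**5. Log-rank over the longer-of window.** With one c for all patients, simulation (4,000 trials per case, 184 per arm) gives 2.1–3.0% per side with no effect, and 83–86% power. With varying c, control's risk set after month 12 holds only patients with c above 12, while the test arm's at time t holds those with c above t−12. If long-c patients are at higher risk, late control risk sets are enriched with them.
- c of 3 or 18, doubled hazard at 18, f = 1: false benefit 4.4% against 2.5%.
- c of 1/6/24 in 50/25/25% of patients, threefold hazard at 24: 5.4% at f = 1, about 3.4% at f = 0.25.
- The shift disappears when c never exceeds 12, or when both arms run to c+12.

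**6. Price of each common window.** If the effect starts only when the regimens diverge at month c, simulated log-rank power at c = 1/3/6/12 is 74/50/21/3% for fixed 12 months. With both arms followed to c+12 it is 75/54/27/6% at f = 0.25 and 76/63/43/20% at f = 1.

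**The case against.** The best defence is that the plan can be read coherently. Section 20 and the 49% rate point to month 12, the sample size reproduces as a two-proportion comparison at one time, and Section 19 supplies a two-sided chi-square. Read that way there is no window bias. This much stands, so a reader should not infer that the plan contains no valid between-arm test: chi-square is valid at a common time. It does not settle the matter, because four places define a different window and Section 20 states its own criterion, which is not reconciled with Section 19.

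Other stronger readings also fail:
- **A log-rank test alone cures the problem.** Step 5 shows it need not. Section 6 sets c by device, coronary history and acute coronary syndrome with no upper limit, so prognostic c above 12 months is possible. The documents do not show how common it is.
- **The late hazard can be taken from the background rates in Sections 1 and 3.** Those are segment-specific patency and overall mortality figures, not rates for this composite. Combining the iliac figure with mortality and the 49% rate even implies a negative hazard.
- **The follow-up row of the Synopsis is a third window.** Its phrase "completed a 12-month or end of study treatment follow-up evaluation" says when the trial counts as complete.
- **The direction of the bound rule is unknown.** Section 20 lists success terms, but Section 6 defines failure events, so lower is better.

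On bleeding, Section 20 treats secondary endpoints descriptively, and Section 6 stops study therapy at a first primary event. A contrast of 1 v 13 months at c = 1 therefore describes only patients who complete assigned therapy. The arm dependence remains.

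**Conclusion.** The point holds as an unresolved contradiction that must be fixed before analysis. The arm-dependent window and its conflict with Section 20 follow from the text alone.

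The ambiguity of the bound rule is also firm. Its readings span 0.3% to 48% false success, and none matches the two-sided 0.05 in Sections 14 and 19.

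For raw proportions over the longer-of window, the bias runs against the test arm, but its size is not known. It is nil if the hazard after month 12 is zero and severe if a long c meets a sustained hazard. A reader might infer that the trial is bound to report harm; the documents do not support that, since they give neither input and do not commit to that analysis. The log-rank shift towards the test arm is modest, about 4–5% against 2.5% in the assumed f = 1 cases, and conditional on prognostic c above 12 months.

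**What to change.** 1. Reconcile the Synopsis and Sections 6, 7, 14 and 20 to one primary window, identical in both arms. There are two workable choices:
   - Fixed 12 months. This matches Section 20 and the 49% rate and needs no extra contacts, but the contrast shrinks as c approaches 12.
   - c+12 months in both arms, with c recorded before randomisation. This fits the Synopsis objective, which refers to the end of study therapy. It adds up to min(c, 12) months of control-arm contacts, and the power gain is small if late hazard is low. Table 2 note 4 allows phone visits only after refusal or non-attendance and two documented attempts, so it needs rewording if phone contact is planned.
2. Replace the Section 20 bound rule with one named two-sided 0.05 intention-to-treat comparison on that window: a log-rank test with Kaplan-Meier event rates at the same time in both arms, or chi-square if a fixed 12-month proportion is kept.
3. Use the same common window for the secondary and bleeding summaries, and bring the Synopsis and Section 6 into line.
4. Restate power for the chosen window and an assumed distribution of c, rather than enrol more patients.

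Apart from the optional control contacts, the cost is wording and routine analysis.

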Peripheral catheter interventions are performed under local anesthesia allowing early and full mobilization. However, as a result of this intervention, atherosclerotic plaques are ruptured and platelets aggregate at the site of injury. Extensive vessel wall damage coupled with low shear stress and poor infrapopliteal outflow are mostly responsible for the occurrence of reocclusion.

Additionally, in the initial phase after catheter intervention, a hypercoagulable state prevails, as parameters of activated coagulation, including thrombin-antithrombin complexes (TAT), D-Dimer and Fibrinopeptide A (Fa) become elevated in the plasma. This activated coagulation system produces conditions favorable for early thrombotic occlusion, where 'early' is usually defined as a period covering the first four weeks after the intervention. Subsequently, intimal hyperplasia may follow which is responsible for intermediate and late-term restenosis and reocclusion. Intimal hyperplasia occurs as a result of denudation (tearing off of the inner lining) of the endothelium caused by manipulation of the vessel wall with the catheter. Reported rates of arterial reocclusion or symptomatic restenosis following femoropopliteal PTA are between five and twenty-five per cent for early events and about 40% one year. The five year patency rate was reported to be 83% for iliac and 58% for femoropopliteal PTA, whilst patients with stenoses or occlusions of less than 3 cm had a favorable long-term patency rate of 74%

Patients with CLI or those subjected to local thrombolysis show higher incidences of reocclusion. The implantation of drug-eluting or nitinol stents, or treatment by intravascular brachytherapy following PTA are considered as interventions with the capacity of reducing the occurrence of intimal hyperplasia, however may be associated with delayed endothelialization

and increased risk of thrombosis.

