## 9. Method of assigning subjects to treatment

Patients scheduled for a planned discharge will be randomized on a 1: 1 basis using a central computerized randomization portal available through RedCap® to either of the following treatment groups:

ASA (81 mg/d for U.S. sites; 75-100 mg for international sites) + clopidogrel:for clinically indicated duration with a minimum of 30 days (control arm)

ASA (81 mg/d for U.S. sites; 75-100 mg for international sites) + clopidogrel 75 mg: for clinically indicated duration + 12m (treatment arm)

An inclusion and exclusion checklist needs to be completed via computerized randomization portal available through  $RedCap^{(R)}$  prior to randomization of the subject.

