## **23.Adverse Events**

All Adverse Events (AE) and Serious Adverse Events (SAE) will be reported through EDC and analyzed through study follow-up period.

Term	Definition
Adverse Event (AE)	Any untoward medical occurrence in a subject. This definition does not imply that there is a relationship between the adverse event and the treatment under investigation.
	Note 1: In addition, the definition of AE applies to any event with an onset post- randomization procedure or to any underlying diseases, present at baseline, that exacerbate in severity post- randomization procedure. Therefore, any underlying disease that was present at the time of enrollment is not to be reported as an AE, but any increase in the severity in the underlying disease is to be reported as an AE. This definition includes events occurring in the follow-up period.
Serious Adverse Event (SAE)	
 
An adverse event that:
 
led to death;
 
led to a serious deterioration in the health of the subject that: 
 
resulted in a life-threatening illness or injury,
 
resulted in a permanent impairment of a body structure or a body function,
 
 
 

Clinical events to be considered and reported as expected SAE include, but are not limited to:

- MAE (see definitions)
- Stent Thrombosis
- Bleeding complication as per GUSTO definition
- Vascular event requiring target limb surgical or endovascular intervention or amputation
- Any hospitalization

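### The Synopsis dates the primary endpoint from the index procedure, not from randomisation up to 14 days later, so some pre-randomisation events could count

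*Combined protocol and SAP*

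**What the plan says.** - **Endpoint clock.** The Synopsis (Primary Endpoint) closes its list of components with "death at 12 months from index procedure or end of study treatment, whichever is longer". Section 6 opens its version of the composite without giving a starting point: "The primary endpoint is subject-based of the longer of a 12-month or end of study treatment endpoint of the first occurrence of index limb arterial".
- **Randomisation.** The Synopsis allows it "within 2 weeks of an eligible procedure". Section 9 describes the usual moment: "Patients scheduled for a planned discharge will be randomized on a 1: 1 basis". Section 6 makes randomisation the point at which a subject counts as enrolled.
- **Early events and eligibility.** The complicated-procedure exclusion (Synopsis; repeated in Section 10) covers "need for repeat endovascular, surgical revascularization, amputation or blood transfusion prior to hospital discharge following index procedure", together with perforation, flow-limiting dissection and certain embolizations. It stops at discharge and lists neither MI nor stroke. A separate exclusion removes anyone who had surgery in the preceding 4 weeks.
- **Safety clock.** Section 23 states that "the definition of AE applies to any event with an onset post- randomization procedure".
- **Adjudication.** The events committee list in Section 24 includes MI during the index hospitalization, part of which can precede randomisation.
- **Stopping rule.** Section 6 ends study treatment at the first primary endpoint event.

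**The concern.** In a randomised comparison, outcome counting normally starts at randomisation. Here the only stated origin is the procedure, and the gap can reach 14 days. An event in the gap cannot depend on the assigned duration. If it is counted, it adds the same expected number of events to each arm, shrinks the relative reduction, and uses up that subject's first event, so a later and informative one is lost. A subject randomised later also carries more pre-randomisation time in the window. Read literally, a subject with a gap event would meet the Section 6 stopping rule on entry.

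The sections do not agree on an origin, so sites, the events committee and the analyst could each apply a different rule. The documents describe no placebo, and a counting rule chosen after events are known would be hard to defend.

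**Working it through.** **1. Which components can occur in the gap in a randomised subject?**

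| Component | Position under the current text |
|---|---|
| Death | Impossible |
| Surgical revascularisation | Removed by the 4-week surgery exclusion |
| Amputation above the ankle | Probably removed by the same exclusion, read as surgery |
| Repeat endovascular intervention after discharge | No exclusion written for it |
| Imaged occlusion of the index limb | No exclusion written for it |
| MI, ischemic stroke | No exclusion written for them, before or after discharge |

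**2. The plan's own sample size.** Inputs from Section 14: 49% against 34%, 80% power, two-sided 0.05, 10% dropout. The pooled two-proportion formula gives 169 per arm without continuity correction and 182 with it. The latter is 364 evaluable, and 364/0.9 = 405 randomised. The plan states 368 and 404, so its figure is reproduced closely by the continuity-corrected form.

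**3. A value for q, the share of enrolled subjects with a countable gap event.** This is an assumption. A constant hazard giving 49% at 365.25 days implies

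1 − 0.51^(14/365.25) = 2.5% in a full 14 days (about 0.025 × 404 = 10 subjects), and
1 − 0.51^(2/365.25) = 0.4% in 2 days.

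For a constant hazard these are on the high side, because the 49% includes death and surgery, which drop out of the gap. An early peak in risk would push the other way.

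**4. Power.** Keep 49% overall in controls and let an exact 30% reduction act only on events after randomisation.

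- Counted from the procedure: control 0.49; test q + 0.7(0.49 − q) = 0.343 + 0.3q.
- Counted from randomisation, gap-event patients not randomised: control c = (0.49 − q)/(1 − q); test 0.7c.

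With n = 184 per arm and no continuity correction, where p̄ is the mean of p₁ and p₂:

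power = Φ{ [ |p₁ − p₂|√n − 1.96√(2p̄(1 − p̄)) ] / √(p₁(1 − p₁) + p₂(1 − p₂)) }

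At q = 2.5%, counted from the procedure, the rates are 0.49 and 0.3505: (1.892 − 1.368)/0.691 = 0.758, so power is 77.6%. Counted from randomisation, the rates are 0.477 and 0.334: (1.941 − 1.361)/0.687 = 0.844, so power is 80.1%.

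| q | Observed reduction, from procedure | Power, from procedure | Power, from randomisation |
|---|---|---|---|
| 0 | 30.0% | 81.9% | 81.9% |
| 0.5% | 29.7% | 81.1% | 81.5% |
| 1% | 29.4% | 80.2% | 81.2% |
| 2.5% | 28.5% | 77.6% | 80.1% |
| 3% | 28.2% | 76.7% | 79.7% |
| 5% | 26.9% | 72.8% | 78.1% |

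The last column does not return to 81.9%, because removing early events also lowers the control rate. What the change recovers is the difference between the last two columns: about 1 point at q = 1%, 2.5 at 2.5% and 5 at 5%.

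With the plan's rounded 34.0% in place of 34.3%, the figures at q = 0 and at q = 2.5% (from procedure, then from randomisation) are 83.4%, 79.3% and 81.7%. The pattern is the same.

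**The case against.** The strongest reply is that nothing says pre-randomisation events count. The Synopsis phrase can be read as fixing only where the window ends. Enrolment is at randomisation, Table 2 has no adverse event assessment before the 30-day visit, and Section 23 takes onset after randomisation. Many primary components also reach the sponsor through that adverse event route, since Section 23 lists major adverse events and target-limb interventions among the serious events. This stands: a reader might infer that gap events do count as outcomes, but the text supports only that they could. It does not close the point, because no sentence bars them and the events committee is asked to adjudicate index-stay MI.

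Three further stronger readings fail.

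- **All components are exposed.** They are not; step 1 removes death, surgical revascularisation and probably amputation.
- **A later planned stage would itself be an event.** That requires the first stage to be called the index. No section says so, and staged patients are enrolled only after the last planned procedure.
- **The comparison is biased.** Gap events are balanced in expectation, so the effect is dilution.

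On size, Section 3 reports early reocclusion or symptomatic restenosis rates that "are between five and twenty-five per cent for early events", over about four weeks. If half fell in the gap, q would be 2.5% to 12.5%, and at 12.5% power would be 56.3% from the procedure and 71.0% from randomisation. That is not a usable estimate of q. It concerns femoropopliteal angioplasty, while the trial also takes iliac, below-the-knee and stented patients. Restenosis alone is not a primary component, and complicated procedures are excluded.

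Finally, both arms are assigned the same drugs for the clinically indicated period, at least 30 days in controls. The gap therefore only lengthens an existing stretch without contrast, and the power model, which applies the reduction to every later event, is generous in both columns.

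**Conclusion.** The point holds as a misaligned and incompletely defined time origin. The Synopsis anchors the endpoint at the procedure, randomisation may be 14 days later, Section 6 is silent, and four kinds of event in the gap are neither excluded nor barred from counting.

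The consequence is a modest loss of power. At q = 2.5%, power is 77.6%, under the planned 80%, and about 80.1% if counting starts at randomisation. If nearly all subjects are randomised at discharge, the effect is close to nil. These figures rest on an assumed q, a constant hazard, a 30% reduction acting on all later events, and 184 evaluable subjects per arm. The change is worth making because it settles a rule that should not be left until outcomes are known.

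**What to change.** 1. In the Synopsis and Section 6, state that all primary, secondary and tertiary endpoint events are counted from the date of randomisation, in line with the adverse event definition in Section 23.
2. Add one item to the existing eligibility checklist in the randomisation portal (Section 9): no component of the primary endpoint has occurred between the last index procedure and randomisation.
3. Reconcile the Synopsis endpoint, Section 6, Section 23 and the events committee list in Section 24. The reconciliation should cover how the Section 6 rule on ending study treatment applies to an event before randomisation.

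The cost is amendment wording and one portal item. A few otherwise eligible patients are not randomised (about 10 on the 2.5% assumption), and the 12-month date moves by at most 14 days.
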